8.4.5 Pausing Rules

“Pausing” is discontinuation of study intervention/treatment/dosing (agent/placebo/procedure, etc.) in a protocol-defined group or “arm,” until a decision is made to either resume or permanently discontinue such activity. Subjects continue to be followed for safety during a pause.

The pausing criteria for this study include any one or more of the following:

- A subject experiences an SAE that is unexpected (per the investigator’s brochure or product label) and possibly, probably, or definitely related to a study agent;
- A subject experiences 2 grade 3 or greater AEs that are unexpected (per the investigator’s brochure or product label) and possibly, probably, or definitely related to a study agent.

The principal investigators or the CSO may also pause dosing/study interventions for one or more subjects for any safety issue. The study safety oversight bodies (e.g., DSMB, ISM) may recommend a pause to the CSO.

8.4.5.1 Reporting a Pause

If a pausing criterion is met, a description of the AE(s) or safety issue must be reported by the principal investigators within 1 business day to the CSO and the EC according to their requirements. The principal investigators will also notify the DSMB and ISM. In addition, the CSO or designee will notify all other site investigators by email or through the specified pathway.

8.4.5.2 Resumption Following a Pause

The CSO, in collaboration with the principal investigators and DSMB and ISM, will determine if study activities, including agent administration and/or other study interventions may be resumed, and any additional modifications or requirements that may apply, for the impacted subject(s), or whether the events that triggered the pause require expansion to a study halt (see below).

The CSO or sponsor designee will notify the principal investigators of the decision. The principal investigators will notify the EC of the decision according to the EC's process.

8.4.5.3 Discontinuation of Study Agent

A subject who does not resume study agent/intervention/treatment will continue to be followed for protocol-specified safety assessments or as clinically indicated, whichever is more conservative.

8.4.6 Halting Rules for the Protocol

“Halting” is discontinuation of study intervention/treatment/dosing (agent/placebo/procedure, etc.) for all subjects in a study and suspension of enrollment until a decision is made to either resume or permanently discontinue such activity. Subjects continue to be followed for safety during a halt.

The halting rules are:

- Two or more subjects experience the same or similar grade 3 or greater AEs that are unexpected and possibly, probably, or definitely related to a study agent;
OR
- Any safety issue that the principal investigators or the CSO determines should halt the study. The study safety oversight bodies (e.g., DSMB) may recommend a halt to the CSO.

In addition, the FDA, Malian Ministry of Health, FMOS EC, or any regulatory body having oversight authority may halt the study at any time. The DSMB or ISM may recommend a study halt.

8.4.6.1 Reporting a Study Halt

If a halting criterion is met, a description of the AE(s) or safety issue must be reported by the principal investigators, within 1 business day to the CSO and the EC according to their requirements. The principal investigators will also notify the DSMB and ISM. In addition, the CSO or designee will notify all other site investigators by email or through the specified pathway.

8.4.6.2 Resumption of a Halted Study

The CSO, in collaboration with the principal investigators and DSMB and ISM will determine if study activities, including enrollment, study agent administration, and/or other study interventions, may be resumed and any additional modifications or requirements that may apply.

The CSO or sponsor designee will notify the principal investigators of the decision. The principal investigators will notify the EC of the decision according to the EC's process.

8.4.6.3 Discontinuation of Study Agent

Subjects who do not resume study agent/study intervention will continue to be followed for protocol-specified safety assessments or as clinically indicated, whichever is more conservative.

8.5 UNANTICIPATED PROBLEMS

8.5.1 Definition of an Unanticipated Problem

The definition of a UP is provided in section [8.4.1](#).

8.5.2 Unanticipated Problem Reporting

The investigator will report UPs to the FMOS EC according to NIH Human Research Protection Program (HRPP) Policy 801, as described in section [8.6.1](#).

8.6 ADDITIONAL REPORTING REQUIREMENTS

8.6.1 Reporting to the FMOS EC

Non-compliance and other reportable events will be reported to the FMOS EC according to NIH HRPP Policy 801, which requires reporting as described below.

The following will be reported within 7 calendar days of any investigator or individual associated with the protocol first becoming aware:

- Actual or suspected noncompliance.
- Actual or suspected major deviation.
- Actual or suspected UPs.
- New information that might affect the willingness of a subject to enroll or remain in the study.
- Suspension or termination of research activities, including holds on new enrollment, placed upon the research by the sponsor, NIH or NIAID leadership, or any regulatory agency.

Any death of a research subject that is possibly, probably, or definitely related to the research must be reported within 24 hours of the investigator becoming aware of the death.

Additionally, investigators must provide the following information to the EC in summary format at the time of continuing review, or when otherwise specifically requested by the EC or the Office of Human Subjects Research Protections (OHSRP) Office of Compliance and Training:

- Major and minor protocol deviations.
- Noncompliance reported to the EC that is not related to a protocol deviation.
- AEs and SAEs that do not meet the definition of an UP.

- UPs reported to the EC.

8.6.2 Reporting to the NIAID Clinical Director

The principal investigator will report UPs, major protocol deviations, and deaths to the NIAID clinical director according to institutional timelines.

8.6.3 Reporting Protocol Deviations that Result from the COVID-19 Pandemic

The following addresses the reporting requirements to the FMOS EC with regard to protocol deviations that result from disruption of study visits from the COVID-19 pandemic. These requirements follow the direction of the FMOS EC as well as the NIH reporting requirements. Investigators may modify the protocol without prospective FMOS EC approval when necessary to prevent an immediate apparent harm to a study subject. Typically, when this occurs the event must be reported to the EC via a Reportable Event Form (REF) within 7 days of the deviation. Given the potential need for this to occur on a much larger than usual scale, it is not required that all planned deviations be reported to the FMOS EC in an expedited timeframe. Only those deviations which meet the definition of a major deviation will require reporting, as defined in section 8.4.1.

If a subject cannot complete a protocol-specified study visit or intervention, the principal investigator should assess the impact of the missed visit on the safety of the subject and the scientific validity of the trial. If in the principal investigator's determination neither of these are meaningfully impacted by the deviation, these do not need to be reported to the FMOS EC in an expedited manner. The event should be included in the summary of events reported at the time of continuing review.

If in the opinion of the principal investigator the missed visit or intervention poses a risk to the safety of the subject, the investigator should develop a plan to minimize the impact of the deviation. For example, if the subject is scheduled to return to the study site for safety lab work, the investigator may arrange for labs to be drawn at a location closer to the subject's home. In cases such as this, if the change is necessary to assure the safety of the subject, the investigator may implement the change without prospective FMOS EC approval. If the change meets the definition of a major deviation, it must be reported via a REF within 7 days.

9 STATISTICAL CONSIDERATIONS

9.1 STATISTICAL HYPOTHESIS

The hypotheses are that L9LS will be safe and will confer protection against Pf infection. The primary objective is to evaluate the safety, tolerability, and efficacy of L9LS compared to placebo.

Primary Endpoints:

- Incidence and severity of local and systemic AEs occurring within 7 days after the administration of study agent

- Pf blood-stage infection as detected by microscopic examination of thick blood smear for 24 weeks after administration of study agent. The primary efficacy endpoint will be the time to first infection during the 24 week follow-up.

Secondary Endpoints:

- Pf blood-stage infection as detected by RT-PCR for 24 weeks after administration of study agent
- Measurement of L9LS in sera of recipients

9.2 SAMPLE SIZE DETERMINATION

9.2.1 Sample Size Considerations for Safety Evaluation

The ability of the study to identify safety events can be expressed in terms of the probability of observing 1 or more event of interest (e.g., AEs) within each arm. Within a group of 72 participants, there is over a 90% chance to observe at least 1 AE if the true rate is at least 0.032 and over a 90% chance to observe no AE if the true rate is no more than 0.001. Probabilities of observing 0 or more than 1 AE in a group of size 72 and 48, the number of participants in each weight group and the number of female participants in each weight group, respectively, are presented in [Table 3](#) for a range of possible true event rates.

Table 3. Probability (Pr) of events for different safety scenarios within a group (n=72 or 48).

True event rate	n=72		n=48	
	Pr(0)	Pr(>1)	Pr(0)	Pr(>1)
0.005	0.697	0.051	0.786	0.024
0.01	0.485	0.162	0.617	0.083
0.02	0.233	0.423	0.379	0.249
0.035	0.077	0.722	0.181	0.504
0.05	0.025	0.881	0.085	0.699
0.1	0.001	0.995	0.006	0.960
0.15	<0.001	>0.999	<0.001	0.996

9.2.2 Sample Size Considerations for Efficacy Evaluation

The study is designed to evaluate protective efficacy of L9LS at 900 mg by testing the null hypothesis,

H₀: protective efficacy = 0%,
versus the alternative hypothesis,
H₁: protective efficacy ≠ 0%.

The sample size consideration is primarily based on the power of the comparison of L9LS recipients in each weight group with the placebo recipients. Assuming a dropout rate of 10%, Table 4 presents the power assuming an exponential proportional hazards model with a 2-sided significance level of 0.05 over a range of possible protective efficacy and 24-week infection rates under placebo, where efficacy is 1 minus the ratio of the infection rate under L9LS over the

infection rate under placebo. With 72 L9LS recipients in a weight group and 72 placebo recipients, the trial has over 90% power to claim protective efficacy of L9LS if the underlying efficacy is greater than or equal to 0.6 and the infection rate under placebo is no less than 0.5. When restricted to female participants, with 48 female recipients of L9LS in each weight group, the trial has over 80% power to claim protective efficacy of L9LS if the underlying efficacy is greater than or equal to 0.6 and the infection rate under placebo is no less than 0.5. Of note, the infection rate under placebo in the phase 2 trial of CIS43LS at the same study sites was 78.2%.^[9]

Table 4. Power for efficacy evaluation under a 2-sided type I error rate of 0.05 assuming a dropout rate of 10%.

Sample size per arm	Infection rate under placebo	Protective efficacy	Power (%)
72	0.5	0.6	93
	0.5	0.7	98
	0.5	0.8	100
	0.6	0.6	98
	0.6	0.7	100
	0.6	0.8	100
	0.7	0.6	100
	0.7	0.7	100
	0.7	0.8	100
48	0.5	0.6	81
	0.5	0.7	91
	0.5	0.8	96
	0.6	0.6	90
	0.6	0.7	96
	0.6	0.8	99
	0.7	0.6	96
	0.7	0.7	99
	0.7	0.8	100
40	0.5	0.6	73
	0.5	0.7	85
	0.5	0.8	93
	0.6	0.6	84
	0.6	0.7	93
	0.6	0.8	97
	0.7	0.6	92
	0.7	0.7	97
	0.7	0.8	99

Table 5 presents the minimum detectable difference between two arms assuming an exponential proportional hazards model, with 2-sided type I error rate of 0.05 under a range of infection rates in the high infection arm and a 10% dropout rate.

Table 5. Minimum detectable difference in the infection rate between two arms under a 2-sided type I error rate of 0.05 assuming 10% dropout rate.

Sample size within each arm (#)	Infection rate (in high infection arm)	Detectable with 80% power		Detectable with 90% power	
		Difference	Infection rate (in low infection arm)	Difference	Infection rate (in low infection arm)
72	0.2	0.164	0.036	0.185	0.015
	0.3	0.203	0.097	0.231	0.069
	0.4	0.228	0.172	0.262	0.138
	0.5	0.244	0.256	0.282	0.218
48	0.2	0.193	0.007	N/A	N/A
	0.3	0.242	0.058	0.275	0.025
	0.4	0.277	0.123	0.317	0.083
	0.5	0.298	0.202	0.346	0.154

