4 STUDY DESIGN

4.1 OVERALL DESIGN

This is a phase 2 trial evaluating the safety and tolerability of one-time SC administration of L9LS in healthy adults in Mali, as well as its protective efficacy against naturally occurring Pf infection over a 6-month malaria season. A secondary objective is to determine if SC administration of L9LS at 900 mg (compared to placebo) mediates protection against naturally occurring Pf infection in healthy Malian adult females stratified by weight during a single malaria season as detected from microscopic examination of thick blood smears and RT-PCR.

The primary study hypotheses are that L9LS will be safe and will confer protection against Pf infection. The study will recruit from 3 MRTC clinics, 1 in Torodo, 1 in Faladje, and 1 in Kalifabougou. All day 0 visits will take place at Kalifabougou for all subjects, regardless of residence.

The rural village of Kalifabougou is situated 46 km from the MRTC laboratory in Bamako where biological samples collected for this protocol will be processed and stored. Torodo is located 12 km north of Kalifabougou, and Faladje is located 25 km north of Kalifabougou. The economy is based on subsistence farming. Kalifabougou, Faladje, and Torodo are similar in terms of geographic, demographic, and epidemiological characteristics, and all three typically experience intense seasonal Pf transmission from July through December each year.[\[22\]](#) Based on data collected in Kalifabougou from 2011 through 2018, 68%-90% of adults who are uninfected (PCR negative) before the malaria season become infected with Pf during the ensuing 6-month malaria season.[\[22\]](#) Accordingly, in the phase 2 trial of CIS43LS at the same study site, 78.2% of participants who received placebo became infected over the 6-month malaria season.[\[9\]](#)

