9.4.4 Efficacy Analyses

Incidence of malaria infection is primarily defined as blood smear–positive Pf infection through 24 weeks after administration, and secondarily as determined by RT-PCR. The efficacy analyses will be MITT.

The primary efficacy analysis will be based on time to the first infection. The survival patterns will be described by Kaplan-Meier curves for each arm. The protective efficacy of the study product will be assessed from the Cox proportional hazards model with study arm as the only regressor and estimated by one minus the hazard ratio. This will be achieved via R package “straweib” that accounts for interval censoring. To address the heterogeneity of the study population, as a sensitivity analysis, a Cox regression with regressors other than the study arm will be additionally performed to account for potential differences among participants. The regressors will include time of enrollment and possibly those covariates that are significantly different between the study product arm and the placebo arm in spite of randomization.

The secondary efficacy analysis will be based on the proportion of subjects who become infected during the 24-week follow-up period. The proportion of subjects who become infected during the 24-week follow-up period will be estimated for each arm and compared across arms based on Kaplan-Meier estimates along with 95% confidence intervals via R package “bpcp.” This estimation accounts for right censoring and the comparison should be equivalent to Fisher’s exact test in case of no censoring. Though not accounting for interval censoring, the Kaplan-Meier estimates are appropriate as the interest is on infection at 24 weeks only.

Protective efficacy of L9LS will be primarily assessed over all participants by comparing all L9LS recipients with placebo recipients. As a secondary objective, the protective efficacy of L9LS will also be assessed among female participants by comparing female recipients of L9LS with female placebo recipients; and a stratified analysis by weight will also be performed. An exploratory analysis will be conducted to assess how the weight-based dosage, in terms of mg of L9LS per kg of subject body weight, affects the protective efficacy. No multiplicity adjustment will be applied to the secondary and exploratory analyses.

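### Do Table 4's power figures mislead because they define efficacy by 24-week infection rates while the primary analysis reports 1 minus the hazard ratio?

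*Combined protocol and SAP*

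**What the plan says.** Section 9.2.2 gives the basis for the sample size: "The sample size consideration is primarily based on the power of the comparison of L9LS recipients in each weight group with the placebo recipients". Table 4 shows power "over a range of possible protective efficacy and 24-week infection rates under placebo", under an exponential proportional hazards model with two-sided 5% significance and 10% dropout. The same sentence defines the effect: "efficacy is 1 minus the ratio of the infection rate under L9LS over the" rate under placebo.

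Two power statements follow directly. With 72 per arm, power is over 90% for efficacy of at least 0.6 and a placebo rate of at least 0.5. For women, with 48 L9LS recipients per weight group, "the trial has over 80% power to claim protective efficacy of L9LS if the underlying efficacy is greater than or equal to 0.6", under the same placebo condition. The section then cites a placebo infection rate of 78.2% in the earlier CIS43LS trial.

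Section 9.4.4 sets out the analysis. In the primary analysis, protective efficacy "will be assessed from the Cox proportional hazards model with study arm as the only regressor and estimated by one minus the hazard ratio". A further analysis works with proportions: "The secondary efficacy analysis will be based on the proportion of subjects who become infected during the 24-week follow-up period". After describing the comparison of female L9LS and female placebo recipients, it adds that "a stratified analysis by weight will also be performed".

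**The concern.** The sample size section and the analysis section use the same term for different quantities. With a common infection the two differ materially, because 1-HR is larger than 1 minus the risk ratio for the same data. A reader who carries the section 9.4.4 definition back to section 9.2.2 would take the 0.6 in the power statements as a hazard-ratio efficacy and would overrate the power at a placebo rate of 0.5. The weight-group comparisons are the stated basis for the sample size, and section 9.4.4 does not spell out which estimator the weight-stratified analysis will report. At stake is whether the power claimed for those comparisons is the power that the planned analysis has.

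**Working it through.** **Inputs (section 9.2.2).** n = 72, 48 or 40 per arm; 10% dropout; two-sided 5%; exponential proportional hazards; placebo 24-week rate p0 = 0.5, 0.6 or 0.7; efficacy PE = 0.6, 0.7 or 0.8. The section does not name its power formula. Freedman's log-rank formula is inferred here because it reproduces the table.

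**Formulas.** On the section 9.2.2 definition:
- p1 = p0(1 - PE)
- HR = ln(1 - p1)/ln(1 - p0)
- expected events d = 0.9n(p0 + p1)
- power = Φ(√d(1 - HR)/(1 + HR) - 1.96)

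**Step 1: reproduce Table 4.** Take p0 = 0.5 and PE = 0.6. Then p1 = 0.2, HR = 0.2231/0.6931 = 0.322, and (1 - HR)/(1 + HR) = 0.678/1.322 = 0.513.
- n = 72: d = 0.9 × 72 × 0.7 = 45.36; 6.735 × 0.513 - 1.96 = 1.495; power 93.3% (table: 93)
- n = 48: d = 30.24; power 80.5% (table: 81)
- n = 40: d = 25.2; power 73.1% (table: 73)

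All 27 cells match, with a largest deviation of 0.48 points. Reading PE as 1-HR in the same formula matches only 5 of 27 cells and is off by up to 16 points. So the table was computed on the definition printed above it.

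**Step 2: convert to the hazard scale.** Implied 1-HR:

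| Placebo rate | PE 0.6 | PE 0.7 | PE 0.8 |
|---|---|---|---|
| 0.5 | 0.68 | 0.77 | 0.85 |
| 0.6 | 0.70 | 0.78 | 0.86 |
| 0.7 | 0.73 | 0.80 | 0.87 |
| 0.782 | 0.75 | 0.82 | 0.89 |

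**Step 3: read 0.6 as 1-HR instead.** Now HR = 0.4 and p1 = 1 - (1 - p0)^0.4. At p0 = 0.5, p1 = 0.242. For n = 72, d = 0.9 × 72 × 0.742 = 48.09; 6.935 × 0.6/1.4 - 1.96 = 1.012; power 84.4%.

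| Placebo rate | n = 72 | n = 48 | n = 40 |
|---|---|---|---|
| 0.5 | 84.4% | 68.0% | 60.1% |
| 0.6 | 90.7% | 76.5% | 68.8% |
| 0.68 | 94.2% | 82.1% | 74.9% |
| 0.782 | 97.0% | 88.0% | 81.6% |
| 0.90 | 98.8% | 93.2% | 88.3% |

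The rates 0.68 and 0.90 are the ends of the seasonal range in section 4.1: "68%-90% of adults who are uninfected (PCR negative) before the malaria season become infected with Pf during the ensuing 6-month malaria season". At 1-HR 0.7, both statements hold even at p0 = 0.5 (94.9% and 83.5%).

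**Step 4: check the formula by simulation.** Freedman's formula is conservative here. Log-rank simulation at 1-HR 0.6 and p0 = 0.5 gives 87-89% (n = 72), 71-74% (n = 48) and 63-66% (n = 40), depending on how dropout is treated. An interval-censored Weibull model on the visit schedule gives 86-89% and 70-75% for n = 72 and 48. By log-rank simulation, 90% with 72 per arm is reached at a placebo rate of about 0.51-0.54, and 80% with 48 per arm at about 0.56-0.60.

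**Step 5: primary comparison, 216 v 72.** At 1-HR 0.6 and p0 = 0.5, d = 0.9(72 × 0.5 + 216 × 0.242) = 79.5. Schoenfeld's formula gives Φ(√(79.5 × 0.25 × 0.75) × ln 2.5 - 1.96) = 94.3%; log-rank simulation gives 97.4%.

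**The case for a change.** The strongest case for a change is that the trial was sized on the weight-group comparisons, and their power is quoted for an effect measure that the primary analysis does not report. At the cited 78.2% placebo rate, a 1-HR of 0.60 is a 24-week risk reduction of only 1 - 0.456/0.782 = 0.42. A reported estimate therefore cannot be set beside the planning value without conversion. At 1-HR 0.6 and placebo 0.5, both power statements fail by formula and by simulation. The female weight-group figure falls furthest, to about 70-75% by simulation.

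The arithmetic stands, and so does the absence of a cross-reference. The conclusion that the reader is left guessing does not. The definition stands beside the table and immediately before both power statements. Planning a time-to-event comparison from cumulative risks under a stated exponential model is ordinary practice, and Table 5 works the same way. The hazard ratio follows in one line. Section 9.4.4 reports both the hazard ratio and the 24-week proportions, so results can be compared with the planning value on its own scale. The weight-stratified clause sits in a paragraph about protective efficacy, a term that section 9.4.4 ties only to 1-HR, so an analyst would report that.

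**Conclusion.** No change follows. The two scales are real, but Table 4 and its two power statements are correct as defined. Efficacy of 0% is the same null on both scales, so the test and its type I error do not depend on the choice. A label or conversion column would alter no result, sample size or conclusion. A note giving the implied 1-HR values is optional.

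The shortfall needs three things together: 0.6 read against the section's own definition, a true 1-HR close to 0.6, and a placebo rate well below the rates that the protocol cites. With 72 per arm at placebo 0.5 it is then about 1-4 points below 90% by simulation; with 48 per arm it is about 5-10 points below 80%.

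This rests on exponential infection times, 10% dropout and the equal arms that Table 4 uses. It also assumes a smear-positive placebo rate near the cited figures. The 68%-90% range describes adults who were PCR negative before the season, so the smear-based rate could be lower.
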